5.3 Restrictions During the Study

These restrictions are required after ASP0598 Otic Solution/placebo administration at Day 1 until completion of the study procedures at Day 57 (SAD), Day 85 (single dose expansion), or Day 85 (MAD), Day 113 (multiple dose expansion), or EOS visit.

- Subjects must refrain from showering or bathing for at least 24 hours after IP administration.
 - Showering or bathing are allowed 24 hours after IP administration. Water precautions are to be taken as per the guidelines in Appendix [12.8](#).
- Any water activities that risk submersion of the ear (e.g., swimming or surfing) are prohibited throughout the entire study period.
- Subjects are not allowed to use any materials (e.g., Q-tips) placed into the ear canal of the treated ear (ear buds or headphones placed at the entrance to the ear canal are considered acceptable). If ear cleaning is desired, then subjects can use a soft tissue placed gently at the entrance to the ear canal.
- Investigators will not clean the ASP0598 Otic Solution/placebo treated ear by suctioning throughout Observation period, unless subjects experience uncomfortable ear discharge. General ear cleaning will be allowed to visualize the whole tympanic membrane at Day 57 (SAD), Day 85 (single dose expansion or MAD), Day 113 (multiple dose expansion) or End of Study (EOS) visit, before imaging picture.

- Investigators may gently remove an obstacle that is blocking the ear canal if it prevents IP application or causes subjects to experience an uncomfortable sensation. If the obstacle is adherent to the tympanic membrane, it should not be removed; it is recommended to wait until the obstacle comes off.
- Subjects should refrain from activities that can increase the middle ear pressure including plane travel (at least 28 days after IP application), positive pressure ventilation (e.g., CPAP or BiPAP) devices, Valsalva maneuvers, excessive high-pressure nose blowing or diving underwater.
- Subject must refrain from activities that can excessively increase body temperature (e.g., Sauna) for 3 days after IP application.
- Subject must refrain from activities that stimulate sweating excessively for 3 days after IP application.

5.4 Screen Failures

A screen failure is defined as a potential subject who signed the Informed Consent Form (ICF), but did not meet 1 or more criteria required for participation in the study and was not randomized.

For screen failures, the demographic data, date of signing the ICF, inclusion and exclusion criteria, AEs up to the time of screen failure and reason for screen failure will be collected in the eCRF.

5.4.1 Rescreening

Results of screening assessments that do not meet the parameters required by eligibility criteria (e.g., clinical laboratory tests, vital signs, physical examination, ear examination, etc.) may be repeated once within the 28-day screening period without the need to register the subject as a screen failure. If more than 28 days elapses from the date of signing the ICF, the subject must be documented as a screen failure. In order to re-screen, a new ICF must be signed and the subject entered into screening with a new subject identification number. Rescreening is only allowed once for an individual subject.

6 INVESTIGATIONAL PRODUCT(S)

6.1 Investigational Product(s) Administered

Table 7 Investigational Product(s)

| | | |
|-----------------------------|--|--|
| Name | ASP0598 Otic Solution | Buffered Aqueous Solvent with Copolymer |
| Use | Test Product | Placebo |
| Dosage Formulation | Liquid for reconstitution and administration | Solution for administration |
| Physical Description | Colorless to pale yellow, clear to slightly opalescent liquid solution | Colorless to pale yellow, clear to slightly opalescent liquid solution |
| Unit Dose Strength | 0.2, 1.0, 5.0, and 15.0 µg/mL | N/A |

Table continued on next page

| | | |
|-----------------------------------|---|---|
| Packaging and Labeling | Clear glass, single-use vial with a rubber stopper and an aluminum crimping cap. | Clear glass, single-use vial with a rubber stopper with an aluminum crimping cap. |
| Route of Administration | Single administration onto the tympanic membrane through the external auditory canal via syringe. | Single administration onto the tympanic membrane through the external auditory canal via syringe. |
| Administration Instruction | See Section 6.4 and Pharmacy Manual and other supporting materials | See Section 6.4 and Pharmacy Manual and other supporting materials |
| IMP or Non-IMP | IMP | IMP |
| Sourcing | Provided centrally by the sponsor | Provided centrally by the sponsor |

Refer to the pharmacy manual and product label for detailed information regarding preparation, handling and storage of the IP and other study treatment(s).

6.1.1 Investigational Product Application

IP (ASP0598 Otic Solution or placebo) will be prepared by the pharmacist or designee according the IRT treatment allocation using the pharmacy manual. The final IP Otic Solution will be brought to the Study Physician or designee in the 1 mL Luer Lock™ syringe. Ensure the final IP Otic Solution is administered within the appropriate window of time, depending on the assigned treatment. Refer to the Pharmacy Manual, Section 9.3, for detailed information. The final IP Otic Solution should be stored at room temperature (20-25°C) and protected from light prior to administration. The following information should be provided by the pharmacist / designee with the final IP Otic Solution as per institutional standards: subject's initials, randomization number, end time of IP preparation, and administer by (time).

The Study Physician or designee will put the 22G sheathed blunt-end needle onto the 1 mL Luer Lock™ syringe prior to administration. The Study Physician or designee should prime the syringe prior to otic administration so that up to a maximum volume of 0.15 mL is applied onto the tympanic membrane.

After ASP0598 Otic Solution or placebo administration, subjects will be required to remain on their side with the treated ear facing up for at least 15 minutes. Please see the Pharmacy Manual, Section 9.4: Dose Administration for detailed instructions.

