6.3 Randomization and Blinding

This is an investigator and subject blinded study. Subjects will be randomized by IRT to receive ASP0598 Otic Solution or placebo in a blinded manner such that neither the investigator nor the subject will know which IP is being administered.

Only the pharmacist and designated staff will be unblinded to treatment. All other study site staff will remain blinded to subjects' treatment assignment.

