6.3.1 Blinding Method

In order to maintain the blind, the ASP0598 Otic Solution and placebo will be received in the same volume and route from the pharmacist or designee. The pharmacist or designee will receive the unblinded treatment assignment from IRT in order to prepare the correct concentration of ASP0598 Otic Solution or placebo. The subject and investigator will be blinded to the treatment assignment.

Dose Escalation

Only one cohort will be enrolled at a time. The randomization number will be assigned based on information obtained from the IRT system.

Dose Expansion

Subjects will be randomized through the IRT system in a 1:1:1 ratio, if 3 treatment groups are selected or 1:1 ratio, if 2 treatment groups are selected based on the interim analysis.

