6.4 Investigational Product Compliance

Single Dose

IP will be administered by the PI or designee on Day 1. Ensure the final IP Otic Solution is administered within the appropriate window of time, depending on the assigned treatment. Refer to the Pharmacy Manual, Section 9.3, for detailed information. Subjects will be provided Ear Care Recommendations (Appendix 12.8) that must be reviewed and acknowledged on Day 1 in the source document. The subject should follow this guidance for the duration of their participation. The investigator will examine the treated ear at every visit.

Multiple Dose

IP will be administered by the PI or designee on Days 1, 15, and 29. Ensure the final IP Otic Solution is administered within the appropriate window of time, depending on the assigned treatment. Refer to the Pharmacy Manual, Section 9.3, for detailed information. Subjects

will be provided Ear Care Recommendations (Appendix 12.8) that must be reviewed and acknowledged at each IP administration visit in the source document. The subject should follow this guidance for the duration of their participation. The investigator will examine the treated ear at every visit.

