7.1.2 Microscopic Ear Examination

The site investigator will examine the tympanic membrane by microscope. TMP closure will be evaluated at all visits except for Screening and Day 1, and will be recorded in the eCRF.

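### The preparation end time and the administer-by time both go with the syringe to staff meant to be blinded, so a use window that differs between arms could reveal the assignment

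*Protocol*

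**What the plan says.** Protocol Section 6.1.1 has the pharmacist or designee prepare the product according to the randomization system's allocation. Then "The final IP Otic Solution will be brought to the Study Physician or designee". The same section instructs: "Ensure the final IP Otic Solution is administered within the appropriate window of time, depending on the assigned treatment". Section 6.4 repeats that instruction under both single dose and multiple dose, and both sections send the reader to Section 9.3 of the Pharmacy Manual for detail. Four items are to be supplied with the syringe, following institutional standards: the subject's initials, the randomization number, and "end time of IP preparation, and administer by (time".

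For single dosing, Section 6.4 says "IP will be administered by the PI or designee on Day 1"; for multiple dosing the same people administer on Days 1, 15 and 29.

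On blinding, Section 6.3 says "neither the investigator nor the subject will know which IP is being administered" and "Only the pharmacist and designated staff will be unblinded to treatment". The stated protections are that active and placebo "will be received in the same volume and route from the pharmacist or designee" (Section 6.3.1) and look identical (Section 6.3.2).

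The site investigator examines the ear by microscope, and "TMP closure will be evaluated at all visits except for Screening and Day 1" (Section 7.1.2). Separately, Section 7.1.1 gives the measurement of perforation size and the evaluation of complete closure to a central imaging vendor.

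**The concern.** Equal volume, route and appearance mask the product itself but not the paperwork that travels with it. If the permitted interval varies by arm and both ends of it reach the person giving the dose, that person may be able to work out the arm. In multiple dosing the cue can recur on Days 1, 15 and 29.

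Safety is the primary objective, and the investigator decides whether each adverse event is related to the product and how severe it is. Every stopping rule in Section 4.1.1.3 turns on relatedness. One rule can be met by a single related severe event of clinical concern in a cohort of 5 or 8. The Dose Escalation Committee works from blinded safety data (Section 4.1.1.2), which presumes that those judgements were made without knowledge of the arm.

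Site-assessed closure is also exposed, and SAP Table 1 tabulates it as both an observed and an imputed response. In the multiple-dose parts only, so is the investigator's discretion under Section 6.6 to skip a Day 15 or Day 29 dose for safety reasons.

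**Working it through.** The plan gives no figure to reproduce, so the check sets the provisions side by side.

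1. **Does the window vary by assignment?** Sections 6.1.1 and 6.4 say it does. Because Section 6.4 says so separately for each regimen, the phrase does not simply distinguish single from multiple dosing. It could still mean active versus placebo, or one concentration versus another.
2. **Are both ends of the window supplied?** Section 6.1.1 supplies both times. Administer-by time minus preparation end time equals the window, provided the window starts when preparation ends. That is the natural reading but is not stated.
3. **Is the recipient blinded?** The syringe goes to the Study Physician or designee, and the PI or designee gives the dose. Under Section 6.3 all site staff other than the pharmacist and designated staff are blinded. Nothing requires the person giving the dose to be unblinded or to make no assessments.
4. **Is there a safeguard?** Sections 6.3.1 and 6.3.2 cover volume, route and appearance. No provision equalises the window, withholds either time or restricts the blinded physician's access to Section 9.3 of the manual, which Section 6.4 cites alongside dosing by the PI or designee.

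What the interval could separate depends on windows that the documents do not give. Escalation cohorts enrol one at a time, each with one active dose and placebo (4:1 in SAD, 6:2 in MAD).

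| Assumed windows | Escalation cohort | Two-arm expansion | Three-arm expansion |
|---|---|---|---|
| Same for all assignments | Nothing | Nothing | Nothing |
| Differ by concentration; placebo carries its cohort's active window | Nothing | Nothing | High from low dose |
| Placebo differs from active; active doses share one window | Active from placebo | Active from placebo | Active from placebo |
| All differ | Active from placebo | Active from placebo | All three groups |

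The second row leaves the placebo window in a three-arm expansion undefined, because two active doses are then in use.

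The planned numbers bound the exposure. SAD has 4 × 5 = 20 subjects and MAD has 2 × 8 = 16, so escalation has 20 + 16 = 36. Two three-arm expansions add 39 + 39 = 78, for a total of 36 + 78 = 114. Exposure therefore runs from 0 subjects (first row) to all 114 if every part opens at full size (last two rows). Under the second row it is 0 in escalation and confined to whichever expansions have three arms, up to 39 subjects each.

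**The case against.** The strongest reply is that the argument depends on a document nobody reading the protocol and SAP can see. A reader might infer that the handover information reveals the treatment group outright. The documents do not support that: the window lengths are only in the Pharmacy Manual, and placebo may simply carry the window of its cohort's active dose. Nor does Table 7 settle it. It lists the active product as needing reconstitution and the placebo as a ready solution, but the synopsis describes the placebo as also being combined with a copolymer before administration. This objection stands, and it makes the conclusion conditional.

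Second, the recipient may be a designee who makes no assessments. That is possible, but the text neither requires it nor prevents the assessing investigator from receiving and giving the product.

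Third, a reader might infer that the efficacy results as a whole are compromised. They are not exposed to the same degree. Complete closure is also read centrally, SAP Table 1 tabulates the central reading beside the site one, and the two perforation-size secondary endpoints come from imaging.

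Fourth, investigator causality does not by itself stop escalation. The Dose Escalation Committee decides, considers cumulative adverse event data from earlier cohorts and may request unblinding. Even so, causality and severity are inputs to its rules, and the central read does not protect them. The Day 15 and Day 29 dosing decisions do not arise in SAD or single dose expansion.

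**Conclusion.** The point holds in conditional form. As written, the treatment-dependent window and the handover of both times in Section 6.1.1 do not sit with the blinding in Section 6.3, and following the text can leak the assignment. Whether it does depends on three things the documents leave open: whether the windows differ between arms that are randomized together, whether the window runs from the end of preparation, and whether the person who sees the times also makes assessments. The size therefore cannot be narrowed below the range from no subject to every subject.

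If there is a leak, its main effect is on adverse event causality and severity, then on site-assessed closure and, in the multiple-dose parts, discretionary skipping of doses. The central reading of closure and perforation size is less exposed. This should be corrected because the gap is plain in the text and the remedy is simple; the documents do not show that the blind has been broken.

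**What to change.** Reconcile Sections 6.1.1 and 6.4 with Section 6.3 in one of these ways:

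- Keep the preparation end time in the unblinded pharmacy record, and give blinded staff only an administer-by time calculated from one window common to all assignments. The sponsor sets its length. Withholding the preparation end time alone only blurs the cue, because the physician still sees when the syringe arrives.
- Require that anyone who sees these times makes no study assessments.
- If the windows are already the same across arms, delete the clause in Sections 6.1.1 and 6.4 that ties the window to the assigned treatment.

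The cost is a minor change to labelling and handling. A common window may also tighten site logistics, but how much depends on the windows in the Pharmacy Manual and cannot be judged from the protocol and SAP.

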6.2 Preparation/Handling/Storage/Accountability

6.2.1 Packaging and Labeling

All IP used in this study will be prepared, packaged and labeled under the responsibility of qualified personnel at APGD or sponsor's designee in accordance with APGD or sponsor's designee standard operating procedures (SOPs), Good Manufacturing Practice (GMP) guidelines, International Council for Harmonisation of Technical Requirements for Pharmaceuticals for Human Use (ICH) Good Clinical Practice (GCP) guidelines and applicable local laws/regulations.

Each carton and vial will bear a label conforming to regulatory guidelines, GMP and local laws and regulations that identifies the contents as investigational drug.

Refer to the pharmacy manual and product label for detailed information regarding packaging, labeling, and preparation of the IP.

6.2.2 Handling, Storage and Accountability

1. The pharmacist or designee must confirm appropriate temperature conditions have been maintained during transit for all IP received and any discrepancies are reported and resolved before use of the IP.
2. Only subjects enrolled in the study may receive IP and only authorized study site personnel may supply or administer IP. Only IP with appropriate expiry/retest dating may be dispensed.
3. All IP must be stored in a secure, environmentally controlled and monitored (manual or automated) area in accordance with the labeled storage conditions and access must be limited to the investigator and authorized study site personnel.
4. The pharmacist, investigator, institution or the head of the medical institution (where applicable) is responsible for accountability, reconciliation and record maintenance (i.e., receipt, reconciliation and final disposition records).
5. Further guidance and instruction on final disposition of used and unused IP is provided in the pharmacy manual.

Refer to the pharmacy manual for detailed information regarding handling, storage and accountability of the IP.

6.3 Randomization and Blinding

This is an investigator and subject blinded study. Subjects will be randomized by IRT to receive ASP0598 Otic Solution or placebo in a blinded manner such that neither the investigator nor the subject will know which IP is being administered.

Only the pharmacist and designated staff will be unblinded to treatment. All other study site staff will remain blinded to subjects' treatment assignment.

6.3.1 Blinding Method

In order to maintain the blind, the ASP0598 Otic Solution and placebo will be received in the same volume and route from the pharmacist or designee. The pharmacist or designee will receive the unblinded treatment assignment from IRT in order to prepare the correct concentration of ASP0598 Otic Solution or placebo. The subject and investigator will be blinded to the treatment assignment.

Dose Escalation

Only one cohort will be enrolled at a time. The randomization number will be assigned based on information obtained from the IRT system.

Dose Expansion

Subjects will be randomized through the IRT system in a 1:1:1 ratio, if 3 treatment groups are selected or 1:1 ratio, if 2 treatment groups are selected based on the interim analysis.

6.3.2 Confirmation of the Indistinguishability of the Investigational Product

The appearance of both the dosage form and packaging of ASP0598 Otic Solution are identical to those of their matching placebo.

6.3.3 Retention of the Assignment Schedule and Procedures for Treatment Code Breaking

The randomization list and treatment assignment blind will be maintained by the IRT system.

6.3.4 Breaking the Treatment Code for Emergency

The treatment code for each randomized subject will be obtained from the IRT system in the event of a medical emergency requiring knowledge of the treatment assigned to the subject. The IRT system will be programmed with blind-breaking instructions that can only be requested by the investigator or sub-investigators designated to have access to perform blind-breaking. In case of a medical emergency, the investigator has the sole responsibility for determining if unblinding of the subject's treatment assignment is warranted. Subject safety must always be the first consideration in making such determination. If the investigator decides that unblinding is warranted, the investigator should make every effort to contact the sponsor prior to unblinding a subject's treatment assignment unless this could delay emergency treatment for the subject.

Prior to the initial IP shipment, the investigator must have confirmed ability to access code-break through the IRT system and must have a designated backup (e.g., redundant processes) to support emergency unblinding requirements.

Prior to randomization, subjects should be provided with information that includes the study site emergency contact number and back-up contact number in case of a medical emergency. Any unblinding by the investigational personnel must be reported immediately to the sponsor and include an explanation of why the IP was unblinded. If unblinding is associated with a serious adverse event (SAE), the investigator is to follow the instructions in [Section 12.4.5 Reporting Procedures for Serious Adverse Events].

Care still be taken to limit knowledge of the treatment assignment, in case this can affect the blinding of other subjects or future study assessment for the subject.

6.3.5 Breaking the Treatment Code by the Sponsor

The sponsor may break the treatment code for subjects who experience a suspected unexpected serious adverse reaction (SUSAR), in order to determine if the individual case or a group of cases requires expedited regulatory reporting. Individual emergency codes will be provided to the limited personnel who are responsible to break the codes for all SUSAR cases for reporting purposes.

6.3.6 Assignment and Allocation

SAD

In each cohort, a total of 5 subjects will be randomized in a 4:1 ratio of ASP0598 Otic Solution (4 subjects) and placebo (1 subject).

MAD

In each cohort, a total of 8 subjects will be randomized in a 6:2 ratio of ASP0598 Otic Solution (6 subjects) and placebo (2 subjects).

Dose Expansion

- Based on the interim analysis results, if 3 treatment groups are selected, approximately 39 subjects will be randomized in a 1:1:1 ratio of high dose ASP0598 Otic Solution, low dose ASP0598 Otic Solution, or placebo (13 subjects in each treatment group).
- If 2 treatment groups are selected, approximately 26 subjects will be randomized in a 1:1 ratio of high dose ASP0598 Otic Solution or placebo (13 subjects in each treatment group).

Subjects will be stratified at the time of randomization by % size of the TMP ($\leq 15\%$, $> 15\%$) at the Screening Visit. Subjects will be balanced equally between the treatment groups.

TMP size group will be determined by the Screening images sent from the investigative site to the central imaging vendor.

For SAD, MAD, and dose expansion, randomization will be performed via IRT using central allocation. If a subject is assigned a randomization number, but does not receive study drug, the randomization number will not be used again. The randomization schedule that determines subject treatment will be computer-generated by IRT before the beginning of the study. The unblinded study site personnel will dispense the treatment according to the IRT system's assignment. Specific procedures for randomization through the IRT are contained in the study-specific IRT manual.

